### **Design and methods**

This was a prospective randomized cohort study and had been approved by the Institutional Ethic Committee of Xuanwu Hospital, Capital Medical University (Beijing, China) in accordance with the guidelines of the 1964 Declaration of Helsinki. Informed consent was obtained from all individuals before collecting any data. From December 2018 through December 2019, the patients who diagnosed as intracranial arterial stenosis or internal carotid arterial stenosis in Xuanwu Hospital, Capital Medical University and Beijing Fengtai You'anmen Hospital were enrolled in this study with random number table. The diagnosis of intracranial arterial stenosis and internal carotid arterial stenosis was confirmed by magnetic resonance angiography (MRA) and/or computed tomographic angiography (CTA). All of the enrolled subjects should comply with the following inclusion and exclusion criteria.

Inclusion criteria: (1) age from 18 to 80 years; (2) diagnosis of ICAS and/or ECAS; (3) NIHSS $\leq$ 4 and mRS $\leq$ 2; (4) signed informed consent.

Exclusion criteria: (1) brain infarction occurring within recent two months; (2) intracranial arterial aneurysm, dissection or malformation; (3) history of cerebral hemorrhage or subarachnoid hemorrhage; (4) history of cerebral trauma; (5) history of other brain injury or disorders; (6) austere diseases such as cancer, heart failure, respiratory failures; (7) respiratory diseases; (8) poor compliance.

The participants underwent 30-minute EEG recording two times. Between the two time recordings, they were randomly performed with NBO (received oxygen supplement with 8L/min, via Venturi mask, maintaining 45min) and rest (had a rest like lying, sitting or walking for 45min), which were labeled NBO group and control group in this study.

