The EEG recording was conducted with an EEG recording equipment (EEG YAL PN-NET, Beijing Yunshen Science and Technology Corporation). Ag/AgCl electrodes were positioned at Fp1, Fp2, F3, F4, F7, F8, Fz, C3, C4, Cz, P3, P4, Pz, T3, T4, T5, T6, O1, O2, A1, A2 (21 channels) according to the international 10-20 system, with electrode impedances all less than 5k $\Omega$ . The sampling rate was 256 Hz for all channels using a 16 bit AD convertor. Channel A1 and A2 were as references. Five minutes of artefact-free data was selected from EEG recordings in each subjects at random, and these participants should maintain awake and lying quietly with eyes closed as much as possible. Data filtering (band pass, 1 to 30Hz) was performed in EEGLAB (version 2019.1) with supplementary scripts operating in the MATLAB

environment. The artefact removal (blink artefact and electromyogram artefact) was performed again automatically using BSS algorithm (sobi) that was implemented into EEGLAB software packages.

The absolute power (AP, with units  $\mu\text{V}^2$ ) was computed using Fast Fourier Transform (FFT) for each electrode over the delta (1-4 Hz), theta (4-8 Hz), alpha (8-13 Hz) and beta (13-20 Hz) frequency bands, and the relative power (RP) was a ratio of the frequency band of interest power to the total power across the 1-20Hz range. The power spectral density (PSD) for each channels was estimated via Welch's procedure with a 2-s Hamming window length. Besides over all channels, fronto-central electrodes (F3, F4, Fz, C3, C4, Cz) which were with mild occipital alpha oscillation impact, were also used to reflect the actual frequency activities in the forehead. Proceeded by python software, the EEG wavelet entropy was calculated via nonlinear dynamics method in order to evaluate the complex of brain function. Power ratio index (PRI) was defined as AP ratios of theta/alpha (TAR), delta/alpha (DAR), (delta+theta)/(alpha+beta) (DTABR), and fronto-central alpha/occipital alpha (FOAR) in this study. Each frequency band AP and RP reduction rate was calculated as a ratio of pre-intervention minus post-intervention bandpower to pre-intervention bandpower.

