### **Statistical analysis**

R software (<http://www.r-project.org>) was used for analysis in this study. The continuous data was expressed as mean $\pm$ standard deviation (SD) or median

(interquartile range, IQR). Dataset following a Gaussian distribution was analyzed with Student's t test; otherwise analyzed with Mann-Whitney U test. As for multiple comparisons among groups, LSD method was used to remove the statistical bias from repeated measure. The comparison between the prior to and post-intervention was performed with paired samples t test and Wilcoxon test. Categorical data was presented as num. (percentage) and proceeded by chi-square test. Multiple analysis using linear regression model was to rule out the confounding effect of other covariates that may affect the EEG measures. p-value  $<0.05$  was indicative of statistical significance.

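### Baseline power is not a stated covariate in any NBO-versus-control comparison of AP or RP, and the mean reduction rate falls below zero when there is no systematic change

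*Combined protocol and SAP*

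**What the plan says.** Design and methods gives every patient a recording before and after the 45-minute interval: "The participants underwent 30-minute EEG recording two times". The analysed segment is a random five minutes: "Five minutes of artefact-free data was selected from EEG recordings in each subjects at random". The same section defines the only measure of pre-to-post change in band power, for AP and RP in every band: "reduction rate was calculated as a ratio of pre-intervention minus post-intervention bandpower to pre-intervention bandpower".

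Statistical analysis gives four relevant rules:

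- Summaries are mean with SD or median with IQR ("The continuous data was expressed as mean" and so on). No rule says which is used for the reduction rate.
- Continuous data: "Dataset following a Gaussian distribution was analyzed with Student's t test; otherwise analyzed with Mann-Whitney U test".
- Within arm: "The comparison between the prior to and post-intervention was performed with paired samples t test and Wilcoxon test".
- Regression: "Multiple analysis using linear regression model was to rule out the confounding effect of other covariates that may affect the EEG measures". No covariate is listed.

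The section does not say whether the post value, the change or the reduction rate is compared between arms. It mentions neither baseline power as a covariate nor a transformation.

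**The concern.** There are two linked issues. First, 1 - post/pre divides by a noisy baseline. Random fluctuation alone pulls its mean below zero, so a mean rate reported for one arm is not a clean percent change. A small true reduction can be largely masked, and an arm with no change can appear to have gained power.

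Second, Student's t test and the Mann-Whitney test cannot adjust for baseline, and the regression does not say that it does. Every patient has a baseline recording, so the plan may leave precision unused. It also leaves open which quantity carries the comparison named in the Objective.

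**Working it through.** The plan has no figure to reproduce. It gives no SD, pre/post correlation, effect size or sample size, so every numerical input below is an assumption.

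**Sign of the mean rate.** Take pre and post as positive and exchangeable, meaning no systematic change. Then E[post/pre] = E[(post/pre + pre/post)/2] ≥ 1, so E[1 - post/pre] ≤ 0. Equality holds only if post equals pre in every patient. Log-normality is not needed for this.

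**Size, AP.** Let log(post/pre) be normal with SD d and true geometric ratio g. The mean rate is 1 - g·exp(d²/2).

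| d | g = 1 (no change) | g = 0.95 (true 5% reduction) |
|---|---|---|
| 0.1 | -0.5% | +4.5% |
| 0.2 | -2.0% | +3.1% |
| 0.3 | -4.6% | +0.6% |

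If s is the SD of log power and r the pre/post correlation on the log scale, then d² = 2s²(1 - r), and the no-change mean is 1 - exp(s²(1 - r)). At s = 0.7 (the value used in the power table below) and r = 0.7, 0.8, 0.9, d is 0.54, 0.44, 0.31 and the mean rate is -15.8%, -10.3%, -5.0%. The power settings therefore imply noisier data than most of the table above.

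**Size, RP.** With logit-normal RP and typical values from 0.40 down to 0.10, the no-change mean is -1.8% to -4.1% (logit SD 0.5, r = 0.8) and -5.6% to -12.2% (logit SD 0.7, r = 0.7). Medians are within 0.05 percentage points of 0.

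**Between arms.** With no treatment effect and equal noise, both arms have the same shift and it cancels; simulated differences in mean rate were -0.1 to 0.3 points. With a true effect, the difference in means is (1 - g)·exp(s²(1 - r)). A 20% fall becomes 0.20 × 1.051 = 21.0 points at s = 0.5, r = 0.8.

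**Precision on the log scale.** With equal variances, the change score has variance 2s²(1 - r) and ANCOVA has residual variance s²(1 - r²). The ratio is (1 + r)/2 = 0.85, 0.90, 0.95 at r = 0.7, 0.8, 0.9. Without adjustment the change score needs 2/(1 + r) - 1 = 18%, 11%, 5% more patients.

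**Power.** Settings: 50 per arm, s = 0.7, 4,000 simulated trials each, two-sided 5%. The two-stage test on the rate is a t test if both arms pass Shapiro-Wilk (an assumed check) and Mann-Whitney otherwise. The adjusted rank test is Mann-Whitney on the residuals of log(post) regressed on log(pre), arms pooled.

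| Log residuals | r, true ratio | Two-stage test on rate | t on log ratio | Log ANCOVA | Adjusted rank test |
|---|---|---|---|---|---|
| Normal | 0.7, 0.75 | 71.6% | 74.3% | 80.4% | 78.8% |
| Normal | 0.8, 0.80 | 68.0% | 70.2% | 74.6% | 72.5% |
| Normal | 0.9, 0.85 | 70.6% | 72.2% | 73.5% | 71.9% |
| t(4) | 0.7, 0.75 | 84.5% | 76.5% | 82.4% | 91.7% |
| t(4) | 0.8, 0.80 | 80.5% | 72.1% | 76.0% | 85.9% |
| t(4) | 0.9, 0.85 | 83.4% | 73.6% | 74.9% | 86.2% |

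The effect ratio was changed with r, so rows should not be compared with each other. Under the null, all four tests rejected in 4.6% to 5.5% of trials.

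Log ANCOVA minus the two-stage test is +8.8, +6.6, +2.9 points with normal residuals, and -2.1, -4.5, -8.5 with t(4). The adjusted rank test minus the two-stage test is +7.2, +4.5, +1.3 (normal) and +7.2, +5.4, +2.8 (t(4)). The Monte Carlo standard error of one power figure is about √(0.7 × 0.3/4000) = 0.7 points.

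**RP power.** This used 2,000 trials and four independent log-normal bands with assumed medians 1:1:3:0.7, s = 0.7, r = 0.7, and an AP ratio of 0.75 in the tested band. For the two-stage test, log ANCOVA and logit ANCOVA, power was 55.3%, 63.5%, 64.5% for delta and 58.0%, 65.7%, 68.1% for alpha. Null rejection was 4.6% to 5.4%.

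**The case against.** The strongest reply is that nothing here is an error. The comparison is randomised, type I error is held, and the shift cancels under the null when noise is equal. The plan allows the median and, for non-Gaussian data, the rank test ("otherwise analyzed with Mann-Whitney U test"), and neither is affected by the shift. If the median follows the non-Gaussian branch, the problem partly limits itself: with 50 per arm and no change, 89% of arms pass Shapiro-Wilk where the shift is 0.5%, but only 42% where it is 4.6%. No section makes the rate a primary outcome or reads an arm mean as evidence of effect. All of this stands, and it is why the point is modest.

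It can also be said that the regression might include baseline power. It might. A reader might infer that baseline adjustment was ruled out; the text supports only that it is not stated.

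A third reply is that the proposed model is not uniformly better. That is also correct: with t(4) residuals log ANCOVA trails the two-stage test in all three settings. The adjusted rank test beats the two-stage test in all six settings shown but is below log ANCOVA in the three normal ones. At r = 0.9 with d of 0.1 to 0.3 and log-normal data, further runs put it level with the two-stage test (73.5 v 73.9%, 74.6 v 75.1%, 73.1 v 72.7%).

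What the reply does not remove is that the plan leaves the compared quantity and the covariates open, permits a mean of a skewed ratio, and does not commit to using a baseline that every patient has.

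**Conclusion.** The point holds as a modest improvement to consider, with medium confidence. The negative mean under no systematic change is a mathematical result; its size depends on assumed noise. Across the AP settings above it runs from -0.5% to about -16%. With normal log residuals at 50 per arm, log ANCOVA gains roughly 2 to 9 power points over the two-stage test on the rate, allowing for simulation error, and least at r = 0.9.

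Three stronger readings are not supported:

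- **That the negative mean biases the NBO-versus-control test.** It does not under the null with equal noise. If noise differed between arms the means would not cancel, but the documents give no information on that.
- **That the lost power comes mainly from the missing covariate, not from the rate.** At r = 0.9 with normal residuals, moving from the rate to the log ratio gains 1.6 points and adding the covariate 1.3. With t(4) residuals, moving to the log ratio loses 8 to 10 points.
- **That an unchanged EEG gives a negative rate.** If post equals pre in everyone, the rate is exactly 0; within-person variation is required. The random five-minute segment makes some variation likely.

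**What to change.** For AP in each band, make the NBO-versus-control analysis a linear model of log(post AP) on arm with log(pre AP) as covariate. Report 100 × (1 - geometric mean ratio) with its 95% CI. For RP, use the same model on the logit scale and report an odds ratio with its 95% CI. Fix the logit scale in advance and do not choose it from residuals.

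As the supporting analysis for heavy tails, prespecify a Mann-Whitney test on the residuals of transformed post regressed on transformed pre, with arms pooled. Show the reduction rate only descriptively, as median (IQR), in every band.

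The cost is a paragraph of SAP text and a short R script, with no new data. Results appear on a less familiar scale. If log residuals are heavy-tailed and only the linear model is used, power can be lower than with the two-stage test on the rate (74.9% v 83.4% at r = 0.9). The rank analysis should therefore be specified alongside it and reported whatever the linear model shows.

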### **Statistical analysis**

R software (<http://www.r-project.org>) was used for analysis in this study. The continuous data was expressed as mean $\pm$ standard deviation (SD) or median

(interquartile range, IQR). Dataset following a Gaussian distribution was analyzed with Student's t test; otherwise analyzed with Mann-Whitney U test. As for multiple comparisons among groups, LSD method was used to remove the statistical bias from repeated measure. The comparison between the prior to and post-intervention was performed with paired samples t test and Wilcoxon test. Categorical data was presented as num. (percentage) and proceeded by chi-square test. Multiple analysis using linear regression model was to rule out the confounding effect of other covariates that may affect the EEG measures. p-value  $<0.05$  was indicative of statistical significance.

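### Gaussian measures are compared between arms with the pooled-variance Student's t test although nothing secures equal arms; Welch's test would remove a minor, conditional error-rate risk at almost no cost

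*Combined protocol and SAP*

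**What the plan says.** Under Statistical analysis, the rule for continuous data is "Dataset following a Gaussian distribution was analyzed with Student's t test"; other data are "otherwise analyzed with Mann-Whitney U test". Pre/post comparisons within patients have their own paired tests. Covariates are handled by a further model: "Multiple analysis using linear regression model was to rule out the confounding effect of other covariates". That section mentions no variance check, Welch correction or robust standard error. R "was used for analysis in this study", but no function or variance option is named. A p-value below 0.05 "was indicative of statistical significance"; sidedness is not stated, and two-sided is assumed here.

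Under Design and methods, patients "were enrolled in this study with random number table", and between the two EEG recordings "they were randomly performed with NBO" or with rest. No allocation ratio, blocking, target sample size or arm size appears. The NBO arm receives one fixed exposure. Control patients "had a rest like lying, sitting or walking for 45min". No SD is given for any measure in either arm.

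**The concern.** Student's t test, as normally understood, pools the two sample variances. Normality and equal variance are separate assumptions: data can be Gaussian in both arms and still differ in SD. With equal arms the pooled standard error is right on average even when the SDs differ. With unequal arms it is too small when the smaller arm is the more variable and too large when the larger arm is.

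The plan meets neither condition by design. Arm sizes are not fixed, and unequal spread is plausible: activity varies within the control arm only, response to oxygen may vary between patients, and outcomes that are ratios or reduction rates can have a spread that moves with their mean. If both inequalities occurred, p-values for the NBO-versus-control t tests would be too small or too large, and confidence intervals too narrow or too wide. The direction could not be known beforehand.

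**Working it through.** The plan contains no sample size, power or SD, so there is no design figure to reproduce. The one stated input is the 0.05 threshold (two-sided critical value 1.96). Arm sizes and SD ratios below are assumptions.

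**1. Large-sample type I error of the pooled test.** With arm sizes n1, n2 and SDs s1, s2:

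- True variance of the difference: Vtrue = s1²/n1 + s2²/n2
- Variance the pooled test uses: Vpooled = [(n1·s1² + n2·s2²)/(n1 + n2)] × (1/n1 + 1/n2)
- Actual error: 2 × [1 − Φ(1.96 × √(Vpooled/Vtrue))]

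Example: arms of 20 and 30, smaller arm with 1.5 times the SD.

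- Vtrue = 2.25/20 + 1/30 = 0.1458
- Vpooled = [(45 + 30)/50] × (1/20 + 1/30) = 1.5 × 0.0833 = 0.1250
- Ratio 0.857, square root 0.926, effective critical value 1.96 × 0.926 = 1.815
- Actual error = 7.0%

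**2. Simulation** (normal data, equal means, 40,000 runs per cell, nominal 5%):

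| Arms | More variable arm | Student, SD ratio 1.5 | Student, SD ratio 2 |
|---|---|---|---|
| 20/30 | smaller | 7.0% | 8.1% |
| 20/30 | larger | 3.4% | 2.9% |
| 18/32 | smaller | 7.8% | 10.1% |
| 18/32 | larger | 3.0% | 2.2% |
| 25/25 | either | about 5% | about 5% |

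Welch's test stayed at 4.8-5.1% in all these cells. Coverage of a nominal 95% interval is 100% minus the error: at 18/32, about 90-92% when the smaller arm is more variable and 97-98% when the larger arm is.

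**3. A milder split.** At 28/32 with the smaller arm more variable, Student's error is 5.8% (ratio 1.5) and 6.2% (ratio 2). With equal SDs it is about 5% at any split.

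**4. How often such splits occur.** The documents state no ratio; simple 1:1 allocation is assumed, so the size of one arm is Binomial(N, 0.5).

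- 40:60 or worse, either direction: 2 × P(X ≤ 16) = 26.8% at N = 40; 2 × P(X ≤ 24) = 15.5% at N = 60
- 18/32 or worse at N = 50: 2 × P(X ≤ 18) = 6.5%, so about 3.2% in the inflating direction

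**5. Average over all splits.** Weighting the formula in step 1 by the binomial probabilities gives 5.1% (ratio 1.5) and 5.2% (ratio 2) at N = 60. Inflating and deflating splits largely cancel.

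**6. Cost of Welch when variances are equal.** At 20/30 with a true effect of 0.8 SD, simulated power is 77.4% for Student and 77.1% for Welch.

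**7. Regression.** The plan gives neither an arm term nor a model form, so any figure depends on an assumed model. In a least-squares ANCOVA with an arm term at 18/32 (4,000 runs per cell), the error was 7.6% and 10.0% with the smaller arm more variable, and 3.3% and 1.8% with the larger. Heteroscedasticity-consistent (HC3) standard errors gave 3.9-5.4%.

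**The case against.** The strongest reply is that nothing in the documents shows unequal spread. This stands. A reader might infer that the contrast of conditions makes unequal SDs likely, but no SD is reported and the mechanisms are weak. Randomisation puts the same mix of stenosis in both arms. The varied rest activities fall between recordings, while the EEG segments are meant to be taken from quiet, awake, eyes-closed periods. Mixed rest would widen the control arm and varied response the NBO arm, so the two could offset each other. Plausible is as far as the text goes.

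A second reply is that both inequalities are needed, marked imbalance is uncommon, and the average error over simple 1:1 splits is about nominal. This stands as a limit on size. It does not remove the point: the trial analyses one realised split, and averaging over splits that did not occur does not recalibrate its p-value or interval.

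Third, if NBO and rest are interchangeable for every patient, both arms share one distribution and the pooled test is close to valid. True, but confidence intervals must also hold when there is an effect.

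Fourth, R's standard t-test function runs Welch's version unless equal variances are requested, so the analysis may already be the better one. The documents do not settle this. If so, the wording needs correcting to match.

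A reader might also infer that every EEG p-value is affected. The text does not support that: non-Gaussian measures go to the Mann-Whitney test and pre/post changes to paired tests. The Mann-Whitney test is no refuge from unequal spread, however. At SD ratio 2 its simulated rejection rate was 5.6% at 30:30, 8.4% at 20:40 with the smaller arm more variable, and 3.3% at 40:20 with the larger arm more variable.

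**Conclusion.** The point holds as a minor, conditional weakness. The plan names a pooled-variance test with no provision for unequal variances and does not secure the equal arms that would protect it. Error and coverage depart from nominal only if the realised arms differ in both size and SD. Under the assumed SD ratios and normal data, that means up to about 8% error at 20/30 and 10% at 18/32 in one direction, and down to about 3% and 2% in the other.

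The documents do not support a claim that the p-values and intervals are wrong, or that the trial's error rate is materially inflated. The actual departure cannot be determined without the arm sizes and SDs. The regression part is secondary because no arm term or model form is specified. What justifies a change is that a test without this dependence is available almost free.

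**What to change.** In Statistical analysis, name Welch's unequal-variance t test in place of Student's t test for NBO-versus-control comparisons of Gaussian measures. This is one line of wording. If variances are in fact equal, the loss is about 0.3 points of power in the case worked above.

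If the linear regression includes an arm term, HC3 standard errors for that coefficient are an optional companion, at the price of slight conservatism in small samples.

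This change does not address the Mann-Whitney comparisons or the paired pre/post tests, and should not be presented as doing so.

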**Official title: The efficacy of normobaric oxygen on chronic cerebral ischemia**

**NCT number: NCT03745092 (<http://www.clinicaltrials.gov>)**

**Date: December 1, 2018**

## **Study protocol**

### **Objective**

The aim of this study was to investigate whether the normobaric oxygen (NBO) could correct the chronic cerebral ischemia (CCI) induced EEG anomalies.

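### LSD cannot remove repeated-measures bias as the plan claims, and, separately, no primary outcome or correction covers plausibly 13 to 25 EEG outcomes, each judged at 0.05

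*Combined protocol and SAP*

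**What the plan says.** The design has two arms, "which were labeled NBO group and control group in this study", and two recordings per person: "The participants underwent 30-minute EEG recording two times". The Objective is to learn whether oxygen "could correct the chronic cerebral ischemia (CCI) induced EEG anomalies"; no single measure is singled out.

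The EEG part of Design and methods defines absolute and relative power in four bands, four power ratios (TAR, DAR, DTABR, FOAR), wavelet entropy, and a reduction rate for each band's absolute and relative power. It uses all channels and also a fronto-central set, but does not say which measures are tested in which region.

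The Statistical analysis section gives t or Mann-Whitney tests for two-sample comparisons, then says: "As for multiple comparisons among groups, LSD method was used to remove the statistical bias from repeated measure". The next sentence handles change over time: "The comparison between the prior to and post-intervention was performed with paired samples t test and Wilcoxon test". A regression follows: "Multiple analysis using linear regression model was to rule out the confounding effect of other covariates". The covariates are not listed. The only decision rule is that a p-value below 0.05 "was indicative of statistical significance".

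**The concern.** Two separate problems sit in one section.

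First, the LSD sentence assigns the method a task it cannot perform. LSD is a rule for pairwise comparisons at the unadjusted level. Whether within-person correlation is respected depends on the error term of the underlying model, and the plan names no such model.

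Second, and more important, nothing limits error across the EEG outcomes. The plan names no primary outcome, ranking or adjustment. It also does not say whether the arms are compared on the post value, the change or the reduction rate. An efficacy conclusion could therefore rest on whichever band, region, ratio or form of the outcome crosses 0.05.

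**Working it through.** The plan states no sample size, overall error rate or number of tests, so it has no figure to reproduce.

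**Counting outcomes** (from the EEG part of Design and methods)
- One region: 4 bands × 2 (absolute, relative) + 4 ratios + 1 entropy = 13.
- Powers in two regions: 4 × 2 × 2 + 4 ratios + 1 entropy = 21.
- Ratios and entropy also fronto-central: 16 + 3 × 2 (TAR, DAR, DTABR) + 1 FOAR + 2 entropy = 25. The text allows this but does not state it.

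Reduction rates, within-arm tests or per-electrode tests would raise the count.

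**False positives across outcomes.** Assume no effect on any outcome, one between-arm test each, and two-sided 0.05 (the plan does not state sidedness).
- Expected number at any correlation, 0.05 × k: 0.65 / 1.05 / 1.25 for k = 13 / 21 / 25.
- Independent, 1 − 0.95^k: 0.487 / 0.659 / 0.723. For normal test statistics this is an upper bound.
- Common correlation r, with c = 1.960: 1 − ∫ φ(u) [Φ((c − √r·u)/√(1−r)) − Φ((−c − √r·u)/√(1−r))]^k du.

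| Outcomes | Independent | r = 0.5 | r = 0.9 |
|---|---|---|---|
| 13 | 49% | 33% | 14% |
| 21 | 66% | 43% | 16% |
| 25 | 72% | 47% | 16% |

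**What LSD does here**
- *Two arms.* With two groups the one-way ANOVA and the t test gave the same p-value (0.1096 from both in a numerical check). LSD is then simply the t test.
- *Four arm-by-time cells, pooled error, no F test.* Simulated under the null with an assumed 40 per arm, at least one false positive among the six comparisons occurs in about 20% / 14% / 11% of trials at within-person correlation 0 / 0.5 / 0.7. Before/after size is 2(1 − Φ(1.960/√(1−r))) = 5.0% / 0.6% / 0.03%, which is too conservative whenever the recordings are positively correlated.
- *Same cells, with a prior F test.* The error under the global null is about 4% to 5%.
- *Repeated-measures model with a within-person error term.* Before/after size is about 5% at all three correlations.

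The last three results show that any LSD harm depends on choices the plan leaves open. The table of outcomes does not depend on LSD at all.

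**The case against.** The strongest defence is that the LSD sentence is only badly worded. Groups in this plan means the two arms, where LSD is harmless, and before/after change goes to paired tests. If LSD follows a repeated-measures analysis, pairing is respected; if it follows an F test, error under the global null is held. This stands, and it reduces the LSD half to a sentence that is wrong and redundant. A reader might go further and infer that LSD inflates error, or misses real before/after changes, however it is run. The documents do not support that: it needs pooled error for the missed changes and no F test for the inflation, and neither is stated. A reader might also take LSD as the plan's intended correction across EEG outcomes, but the sentence concerns groups only.

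On multiplicity, one can say that EEG measures are strongly correlated, that no correlation is documented, and that the study may be exploratory. The correlation point stands in part: the independent figures are upper bounds and the range is wide. Yet even at 0.9 the error is about three times the nominal 5%. The document nowhere calls itself exploratory, and its title speaks of efficacy.

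The reduction rate is an evident candidate for the between-arm measure of band power. It does not cover the ratios or entropy, and the Statistical analysis section never says that it is the quantity tested.

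**Conclusion.** The point holds in two parts of unequal weight. The LSD sentence states a purpose the method cannot serve and adds no valid step; its practical harm is conditional. The defect that must be fixed is the absence of a primary outcome or any correction across plausibly 13 to 25 outcomes. The chance of at least one false positive between arms then runs from 14% (13 outcomes, correlation 0.9) to 72% (25 outcomes, independent), against a nominal 5%.

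These figures assume no effect on any outcome, one two-sided test per outcome and, apart from the independent case, a common correlation. The correlations are assumptions. So is the count of 25, which needs ratios and entropy to be computed fronto-centrally as well.

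A reader might infer that outcomes were in fact picked after the results were seen. The documents contain no results and do not show this. They show only that the plan would permit it.

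**What to change.** 1. Delete the LSD sentence.
2. Rest the efficacy conclusion on the between-arm comparison and use the paired tests for within-arm description only.
3. Name one between-arm quantity for every outcome: the post value adjusted for its baseline, in the linear regression the plan already includes. Use the log scale for skewed powers and ratios, with a rank-based or permutation check in place of the Mann-Whitney route.
4. Report the reduction rates descriptively. They re-express the same before and after values, so each measure is then tested once.
5. List the outcomes and the region for each.
6. If a version dated before data review names a primary outcome, test it at two-sided 0.05 and treat the rest as one family under Holm or a max-T permutation of arm labels. Otherwise apply Holm or max-T to the whole family, report adjusted p-values and label the EEG results exploratory. The second route looks the more likely: the title block carries "Date: December 1, 2018", yet the methods are in the past tense and cite a 2019.1 software version.

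The cost is SAP wording and a few lines of R, with no new data, plus stricter thresholds. Holm starts at 0.05/k = 0.0038 / 0.0024 / 0.0020 for 13 / 21 / 25 outcomes. An outcome with 80% power at 0.05 has a standardised effect of 1.960 + 0.842 = 2.802. Its power at Holm's first step is Φ(2.802 − 2.891) / Φ(2.802 − 3.038) / Φ(2.802 − 3.090), or about 46% / 41% / 39%. Max-T uses the correlation between outcomes and is expected to be milder.

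### No NBO-minus-control estimate or confidence interval is planned and no sample size is stated, so on the rank-test branch a non-significant EEG result cannot be told apart from low precision

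*Combined protocol and SAP*

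**What the plan says.** The Objective is to find out whether normobaric oxygen can correct EEG abnormalities in chronic cerebral ischemia. Under Design and methods, participants are randomised between oxygen and rest, "which were labeled NBO group and control group in this study". The only information bearing on trial size is the enrolment window, "From December 2018 through December 2019", at two hospitals. No target number, power or detectable effect is given.

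The same section defines many EEG measures: absolute and relative power in four bands, over all channels and over the fronto-central electrodes, four power ratios, and wavelet entropy. It also defines a per-patient reduction rate for absolute and relative band power, (pre − post)/pre.

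The Statistical analysis section plans these outputs:

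- Description: "The continuous data was expressed as mean" and SD, or median and IQR.
- Two-sample tests: "Dataset following a Gaussian distribution was analyzed with Student's t test; otherwise analyzed with Mann-Whitney U test".
- Pre/post tests: "The comparison between the prior to and post-intervention was performed with paired samples t test and Wilcoxon test".
- A linear regression to deal with confounding covariates. No treatment term, coefficient or interval is mentioned.
- A threshold: p below 0.05 "was indicative of statistical significance".

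**The concern.** The Objective concerns how far oxygen moves the EEG, which is a question about the size of the randomised contrast. The plan attaches no estimate and no interval to that contrast. The only comparison tied by name to the intervention is the pre/post one, which is not a comparison between arms.

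Followed as written, the plan can classify each measure as significant or not, but it does not say which between-arm effects the data exclude. SD and IQR within an arm describe the spread between patients, not the uncertainty of the difference between arms. With no stated size, a reader has no advance indication of how precise the comparison will be.

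**Working it through.** **No figure to reproduce.** The documents give no sample size, power, effect size or SD. The check therefore has two parts: what a reader could recover from the planned outputs, and how much precision could vary.

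**1. What the planned outputs allow**

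- *Size of effect, band power.* If the reduction rate is summarised by arm, the difference between the two arm means is a rough effect size on a proportional scale.
- *Size of effect, ratios and entropy.* The reduction rate is defined only for band power. No change measure is defined for the four ratios or for entropy.
- *Precision, t-test branch.* With mean, SD and n for each arm, an unadjusted interval is (difference in means) ± t(0.975, n1+n2−2) × pooled SD × √(1/n1 + 1/n2). For the reduction rate, the SD reported is already that of a change measure.
- *Precision of raw change from separate pre and post SDs.* This needs the within-patient correlation r, because SD²(change) = SD²(pre) + SD²(post) − 2 × r × SD(pre) × SD(post). The plan does not call for r or for SDs of raw change.
- *Precision, Mann-Whitney branch.* Two medians, two IQRs and a p-value give neither the location shift nor its interval without further distributional assumptions.
- *Regression.* It could give an adjusted group coefficient with a standard error, but only if group is a term and the coefficient is reported. Neither is specified.

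**2. How much precision could vary**

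Assumptions, none of them from the documents: n per arm, 1:1 allocation, two-sided 5% level, differences in SD units.

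Half-width of the 95% interval = t(0.975, 2n−2) × √(2/n).

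For n = 25: t(0.975, 48) = 2.011 and √(2/25) = 0.283, so the half-width is 2.011 × 0.283 = 0.57 SD.

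Power for a true difference of 0.5 SD is taken from the noncentral t distribution with 2n−2 degrees of freedom and noncentrality 0.5 × √(n/2).

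| n per arm (assumed) | 95% half-width (SD) | Power for 0.5 SD |
|---|---|---|
| 15 | 0.75 | 26% |
| 20 | 0.64 | 34% |
| 25 | 0.57 | 41% |
| 30 | 0.52 | 48% |
| 40 | 0.45 | 60% |
| 50 | 0.40 | 70% |
| 100 | 0.28 | 94% |

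At 25 per arm, an observed difference of exactly zero (p = 1) would still be compatible with effects of up to 0.57 SD in either direction. At 100 per arm the same observation would exclude an effect of 0.5 SD. On the rank branch, the planned output does not show which of these situations applies. The half-widths are for a t interval. They are only a guide to the rank-based interval, whose width depends on the shape of the data.

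**The case against.** The strongest reply is that little is lost, and several parts of it stand.

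- The reduction rate is an effect measure, so a reader who inferred that a significant result would carry no size at all would be wrong for band power.
- On the t-test branch an unadjusted interval can be rebuilt from mean, SD and n. The documents therefore do not support the reading that no null result could be told apart from too few patients. That holds fully only on the Mann-Whitney branch.
- A regression is planned and could supply the missing contrast. It is under-specified, not absent.
- R's t.test returns an interval by default. That makes the remedy cheap, but it does not make the interval a planned output. wilcox.test gives an interval only when asked.

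Two further inferences are tempting and not supported. A reader might conclude that calendar dates determined the size of the trial; the text says when patients were enrolled, not that the dates fixed the number. A reader might also conclude that the plan treats p ≥ 0.05 as evidence of no effect; it sets a threshold for significance and is silent on how a result above it will be described.

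It can also be said that the illustration contains no trial figure, so how serious the gap is depends on an unstated N. That is correct, and it is why the range is extended to 100 per arm.

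**Conclusion.** The point holds in a limited form. No between-arm estimate or interval is pre-specified, the regression's treatment term is not stated, and no sample size is given. On the rank branch these gaps leave a non-significant result uninterpretable as to precision. On the t-test branch a reader could recover an unadjusted interval, but the plan does not provide one.

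The size can only be bracketed: half-widths of 0.75 to 0.45 SD for 15 to 40 per arm and 0.28 SD for 100 per arm, under assumed equal arms, a two-sided 5% level and SD units. The planned tests remain usable. What changes is what can be concluded from a result that misses the threshold. This is a change that should be made to the reporting plan, not a flaw that invalidates the design.

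**What to change.** For each EEG measure, report the NBO-minus-control difference in change with a two-sided 95% confidence interval:

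- From the planned linear regression, with randomised group and the pre-intervention value of the measure as terms. Modelling the post-intervention value or the change (post − pre) gives the same group coefficient once the pre-intervention value is included.
- Where the rank test is kept, the Hodges-Lehmann shift between arms in the change, with its interval (wilcox.test with conf.int=TRUE).
- State the sign convention, since a positive reduction rate means a fall in power.
- Describe p ≥ 0.05 as 'not shown', and list the effects that the interval still allows.

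The plan contains no log transformation, and this change does not need one.

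The cost is a few sentences in the Statistical analysis section and one extra column per table, in the software already named. No patients or procedures are added. The drawback is a large number of intervals. Counting each ratio and entropy once, there are 4 bands × 2 (absolute, relative) × 2 regions + 4 ratios + 1 entropy = 21. They would be unadjusted for multiplicity and should be labelled as such.
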